4.3 Study Enrollment Procedures

This study involves recruitment of 200 HIV infected men and women with evidence of anal dysplasia from the Anal Dysplasia Clinics. This study will be available for enrollment at Thomas Street Clinic (TSC), Baylor College of Medicine and at the Mount Sinai Anal Dysplasia Clinic. In order to recruit these subjects, we will distribute information to both clinics and also physicians and their clinical staff who are in charge of the care of the subjects. The subjects will talk with their own physician who will describe the study, and arrange for an appointment. After their questions have been addressed, women who remain interested will sign the informed consent form. Potential participants will be approached by a trained research assistant (RA) to determine eligibility. Patients who participate in the study and are identified with anal disease will have access to appropriate ongoing care after study completion and will be offered remuneration for travel and inconvenience.

Potential subjects will read the informed consent. The consenting clinician will answer all their questions. The subject will be given a copy of the signed consent. The signed consent will be kept in a locked cabinet at the clinical site. We will explain all the procedures that will be performed, possible risks, benefits and alternatives.

Once the patient is enrolled, their information will be entered in the OnCoreTM Database System, which is a collection of interrelated tables that contain information on various aspects of enrollment activities. Information about human subjects will only be available to the research clinicians of the originating site. There is a potential loss of confidentiality at these gatherings, so participants will be counseled regarding the loss of confidentiality and this risk will be documented in the informed consent form.

5. STUDY INTERVENTIONS

5.1 Interventions, Administration, and Duration

Study Drug – Proflavine Hemisulfate

Proflavine was used under FDA IND #102217; the HRME itself is an IDE-exempt device by the FDA. The contrast agent, proflavine, used in this study is the principal component of acriflavine and has been used for fluorescent imaging in the European, Asian and Australian gastrointestinal literature without any adverse events.

Study Intervention - mobile High Resolution Microendoscope (mHRME)

Patients will have mHRME images taken of Lugol's negative (abnormal) areas and subsequent standard-of-care HRA biopsies at each image site. In addition, there will be at least one extra image and biopsy taken at a Lugol's positive (normal) site. Each patient will likely have ≥ 2 biopsies. We plan to enroll 200 patients, which will yield 225-300 images.

Our approach uses topical contrast (proflavine) that directly highlights cell nuclei change, the most important pathologic marker of squamous cell intraepithelial neoplasia. In addition, we will implement image-analysis software to highlight these changes in real time, enabling less experienced practitioners to accurately recognize the hallmarks of neoplasia. The high-resolution fiber-optic microendoscope (mHRME) proposed for use here delivers 0.5 mW of 455 nm light to the tissue through a 0.8 mm diameter fiber- optic bundle, corresponding to an irradiance level of 100mW/cm2.

5.2 Handling of Study Interventions

See Manual of Operations (Appendix 1) for detailed instructions of HRME intervention.

5.3 Concomitant Interventions

N/A

5.4 Adherence Assessment

N/A

6. STUDY PROCEDURES

6.1 Schedule of Evaluations

See Appendix 2 for Study Calendar

6.2 Description of Evaluations

See Manual of Operations (Appendix 1) for a detailed description of the Evaluations

6.2.1 Screening Evaluation

All patients scheduled for HRA will be screened for eligibility for the study at each clinic date.

Consenting Procedure

The research population will be identified from patients at Thomas Street Clinic and the Anal Dysplasia clinic at the Mount Sinai Medical Center ([name]) in New York City. The patient will be given information regarding the study and will be given the appropriate amount of time to carefully weigh the risks and benefits of the study. If the patient agrees to consent to participating in the study, the patient/participant will be counseled regarding all alternatives to study enrollment and regarding the right to withdraw consent at any time. In addition, the participant will be reassured that participation in the clinical trial will not in any way affect the future medical care received. The only document linking the participant and the research will be the consent form which will be filed in the subject's medical record.

Screening

The screening will be performed through secure electronic medical record system. The study investigators and study staff will make sure that personal information is kept confidential. All participant information will be stored securely in locked file cabinets in areas with access limited to study staff. All reports, study data collection, and administrative forms will be identified only by a coded number to maintain participant confidentiality. All local databases will be secured with password-protected access systems. Forms, lists, logbooks, appointments books, and any other listings that link participant ID numbers to other identifying information will be stored in a separate, locked file in an area with limited access.

Since [name] is a medical provider at TSHC, this temporary access to patients' PHI to determine eligibility does not constitute more than minimal risk and will not adversely affect the privacy rights and welfare of the individuals who are covered by the waiver. Since [name] is a medical provider at MSSM, this temporary access to patients' PHI to determine eligibility does not constitute more than minimal risk and will not adversely affect the privacy rights and welfare of the individuals who are covered by the waiver.

6.2.2 Enrollment, Baseline, and/or Randomization

Enrollment

Patients who are then found to be eligible and enroll in the study would provide written consent to do so. The patients covered by the waiver (those who are screened for the study but who are found to be ineligible will have no information recorded about them. Patients who refuse enrollment will only have their name and demographic information recorded so that the research coordinators will not recontact them.

Baseline Assessments

See Manual of Operations (Appendix 1) for a detailed description of the Baseline Assessments

Randomization

There is no randomization for any of the objectives in this protocol.

6.2.3 Blinding

NA

6.2.4 Follow-Up Visits

There will be no Follow-up Visits. See Manual of Operations (Appendix 1) for a detailed description of the Follow-up phone Calls.

6.2.5 Completion/Final Evaluation

The study is a single visit study. Patients will be contacted by phone at 1 year and 2 years for follow up evaluation. See MOP for the phone contact details.

7. SAFETY ASSESSMENTS

7.1 Specification of Safety Parameters

We will use Common Terminology Criteria for AE v5.0. Serious adverse events will count as Grade 3 (Severe or Medically Significant, but not Immediately Life Threatening: Hospitalization or Prolongation of Hospitalization Indicated; Disabling; Limiting Self Care ADL), Grade 4 (Life-threatening consequences; urgent intervention indicated) or Grade 5 (Death related to AE).

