7.3 Adverse Events and Serious Adverse Events

Possible risks associated with the study procedures are listed below. There may also be risks that are not known.

Allergic reaction

There is the possibility of an allergic reaction to the Proflavine contrast dye in which participant may have local irritation. The participant can receive antihistamines and other anti-allergy medications if this happens.

Specimen Imaging Probe

There are no known risks from the use of the imaging probe.

Anal biopsies

The risk for anal biopsies are pain, bleeding, and infection. The biopsies are part of the standard of care procedure and would be obtained regardless of study enrollment. It is important that the participant tell the study staff about any side effects that he/she may have had even if he/she does not think it is related to the procedure. Because these patients will all have abnormal anal cytology, the HRA is a standard-of-care procedure.

Pregnancy

Insufficient information is available on the use of Proflavine in pregnancy. Drugs can have harmful effects on the fetus at any stage of pregnancy.

Loss of Privacy

Subjects will be consented on the day of their procedure. Subjects will be taken to a private area where the study information will be discussed. No additional sensitive information will be requested from the subjects beyond what is required to perform a standard study.. Subjects will be given an ID number for all forms, images, and communications. All data will be coded. Source documents will be redacted of all PHI before being sent from outside sites for data monitoring/data entry in the database. All PHI collected on BCM subjects will be stored in locked cabinets or password-protected files/computers where only the PI and study coordinator can see the names. All case report forms will use the assigned subject ID. Since the subject participation is only for one visit, there will be limited opportunity for privacy interests to arise between study recruitment and end of the study. The only extra intrusion of privacy will be an additional phone call at 2 and 30 days after the procedure to ensure that the subject has not suffered any adverse events. During the follow-up, only the study coordinator and/or the PI will have contact with the subject. Information pertaining to the study will only be discussed with the subject and messages containing identifiers of the subject's participation will not be left on voice-mail messages

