7.4 **Reporting Procedures**

PI will inform local and IRB of record within 5 days of SAE reporting. AEs will be reported to the IRB annually at renewal. Any event that is reportable to IRB will also be reported to the DLDCCC Data Review Committee (DRC) via the Patient Safety Officer at [contact].

Any event that is reportable to the BCM IRB must also be reported by the BCM PI to the FDA via safety reports and in the annual report. Unexpected fatal or life-threatening adverse drug experiences will be reported within 7 calendar days. Serious and unexpected adverse drug experiences will be reported within 15 calendar days.

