Serious adverse events will count as Grade 3 (Severe or Medically Significant, but not Immediately Life Threatening: Hospitalization or Prolongation of Hospitalization Indicated; Disabling; Limiting Self Care ADL), Grade 4 (Life-threatening consequences; urgent intervention indicated) or Grade 5 (Death related to AE).

Data Safety Monitoring

We will follow the Cancer Therapy Evaluation Program (CTEP) guidelines for reporting of adverse events. All expedited adverse event reports are required to be submitted to the local Institutional Review Board (IRB) of the reporting institution. Baylor College of Medicine has a standardized system for data and safety monitoring used by all investigators conducting NIH-funded research on patients. This includes a preliminary evaluation by the Dan L. Duncan Cancer Center (DLDCC) PRMC during the scientific review process, and an Institutional Review Board (IRB) review of serious and unexpected adverse events. Additionally, an independent research coordinator from BCM will monitor and review 25% of the data for accuracy , and 25% of all charts at both sites. 100% of adverse events will be monitored by the PI and study team. On site audits will be conducted every 6 months. [name] (Research Coordinator) and [name] will handle all reporting to the FDA for IND for proflavine.

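### Seriousness is defined only through CTCAE Grades 3 to 5, so grade rather than outcome decides which events enter the 5-day IRB report and the 15-day report

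*Combined protocol and SAP*

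**What the plan says.** Section 7.1 names the grading scale ("We will use Common Terminology Criteria for AE v5.0") and then defines an SAE by grade: "Serious adverse events will count as Grade 3 (Severe or Medically Significant, but not Immediately Life Threatening". The Grade 3 text continues with "Hospitalization or Prolongation of Hospitalization Indicated; Disabling; Limiting Self Care ADL", and the definition closes with "Grade 4 (Life-threatening consequences; urgent intervention indicated) or Grade 5 (Death related to AE". The definition in the MOP (Appendix 1) has the same wording, down to "Grade 5 (Death related to AE". Neither place lists criteria for seriousness apart from the grade.

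Section 7.4 builds the reporting routes. SAEs go to the IRB within 5 days, which section 7.6 repeats. For the FDA there is a 7-day route for unexpected fatal or life-threatening drug experiences, and a 15-day route: "Serious and unexpected adverse drug experiences will be reported within 15 calendar days". For the rest, "AEs will be reported to the IRB annually at renewal". A further sentence in 7.4 requires that any event reportable to the Baylor IRB also go to the FDA, through safety reports and the annual report. That sentence has no qualifier for expectedness or for relation to the drug.

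**The concern.** By general safety-reporting convention, grade measures how intense an event is and seriousness describes its outcome. The plan uses one in place of the other, and the choice decides whether an event is reported within days or at annual renewal.

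The route matters more than usual here. Proflavine is given under an IND. Section 7.6 says there is no data safety monitoring board, section 9.4 marks interim analyses and stopping rules as not applicable, and section 10.3.5 has the Data Review Committee look at the study at least once a year. The SAE trigger is therefore the main fast external check. If it sorts events by intensity, a proflavine event that matters by outcome can take the slow route, while expected biopsy discomfort takes the fast one.

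**Working it through.** No arithmetic applies. The check follows the word *serious* from its definition into each reporting route.

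| Route | Trigger as written | Depends on the grade-based definition? |
|---|---|---|
| IRB, 5 days (7.4, 7.6) | SAE | Yes, directly |
| FDA, 15 days (7.4) | Serious and unexpected drug experience | Yes; 7.1 and the MOP hold the only definition of *serious* |
| FDA, 7 days (7.4) | Unexpected and fatal or life-threatening drug experience | No; it uses neither *serious* nor a grade |
| IRB, annual (7.4) | Other adverse events | Yes; it is the default below Grade 3 or with no grade |

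**Events that can be missed.** Take a bleeding event that leads to admission but is graded 2. Under 7.1 it is not an SAE, so its IRB route is the annual one. If it were an unexpected drug experience, it would also fall outside the 15-day report. A second case is a fetal outcome after exposure. Section 7.3 raises that risk ("Drugs can have harmful effects on the fetus at any stage of pregnancy"), but no descriptor in 7.1 covers it. Pregnancy is an exclusion in 4.2, so the case should be rare. In both cases IRB reporting moves from 5 days to as long as the interval between renewals, about 12 months at most.

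**Events that are over-included.** Grade 3 in 7.1 includes limitation of self-care. Brief post-biopsy pain at that level is therefore an SAE with a 5-day IRB report. Being IRB-reportable, it also goes to the FDA under the unqualified sentence in 7.4. Yet section 7.2 anticipates that most events will be pain and bleeding and attributes them to anoscopy, and section 7.3 says the biopsies would be taken whether or not the patient enrolled.

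**Does other text close the gap?** Three places come near.

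- MOP steps 20 and 21: any adverse event reported on the Day 2 or Day 30 call reaches the PI within 24 hours, whatever its grade. This notice is internal, and the SAE form then follows only where applicable, under the same definition.
- MOP, data safety monitoring: reporting is to follow CTEP guidelines, whose content is not given and which are not reconciled with 7.1 or 7.4.
- Section 7.6: reporting to the review committee and the FDA follows those bodies' policies, again without content.

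None of the three restates what *serious* means.

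**The case against.** The strongest reply is that 7.1 is less severity-bound than it looks. Hospitalization or its prolongation, disability, life-threatening consequences, death and medical significance are all named in the grade text, so a careful grader would place most outcome-serious events at Grade 3 or above. This stands, and it makes the gap narrow. It does not close it: those terms describe a grade, so the route still depends on the grade assigned, and congenital anomaly is absent.

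A second reply is that over-reporting leaves no participant unprotected, and that MOP steps 20 and 21 have the PI inform the IRB if needed, which suggests some discretion. The first half is fair. The second is not repeated in 7.4 or 7.6.

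A third is that events do not go unseen for a year. The PI hears within 24 hours of what is reported on a call, weekly meetings present adverse events, and on-site audits are six-monthly. That is right. The delay concerns external reporting only.

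Four stronger inferences are tempting, and the documents do not support them.

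- *The 7-day clock is affected.* It has its own trigger, so the grade rule neither adds events to it nor removes them.
- *Deaths unrelated to the study are missed.* The Grade 5 wording concerns death resulting from an adverse event. The remark in 7.2 about recording events regardless of relatedness concerns attribution to the study procedure. These are different relations, so there is no contradiction.
- *Expected biopsy pain floods the 15-day report.* That report needs an unexpected drug experience. Anticipated pain attributed to anoscopy does not qualify. It reaches the FDA only through the unqualified sentence, which sets no clock.
- *The SAE rate cannot be compared with the earlier proflavine experience in 7.2.* That statement claims no related adverse events of any kind, so the definition of *serious* cannot alter it.

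**Conclusion.** The point holds in a limited form. The only stated definition of an SAE is a grade threshold. It governs the 5-day IRB report and, through the word *serious*, the 15-day report. As written, it can send outcome-serious events graded 1 or 2, or ungraded, to annual IRB reporting, and it sends brief severe biopsy pain into the 5-day report and on to the FDA.

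For a misrouted event the size is a wait of up to about 12 months instead of 5 days at the IRB, or instead of 15 days for an unexpected drug experience. How many events this would touch cannot be estimated, because the documents give no rate of Grade 3 pain or of low-grade serious events. The sample size, outcomes and analyses are unaffected.

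The conclusion rests on two assumptions: that seriousness is properly judged by outcome, which is general convention and not stated in the plan, and that staff apply the explicit rule in 7.1 and the MOP rather than an unstated definition from the cited policies.

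**What to change.** 1. In 7.1 and the MOP, define seriousness by outcome at any grade: death, life-threatening event, hospitalization or its prolongation, disability, congenital anomaly, or an important medical event. Keep the CTCAE v5.0 grade as a separate severity field.
2. In 7.4, reconcile the sentence that sends every IRB-reportable event to the FDA with the 7-day and 15-day triggers, so that each clock names its own criterion.
3. Align the CTEP reference in the MOP with the same definition.

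Asking about pregnancy on the Day 30 call would be a reasonable addition, but it is new data collection and not part of this correction.

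The cost is a wording amendment, one seriousness field on the adverse event form, and one added judgement per event.

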7.2 Methods and Timing for Assessing, Recording, and Analyzing Safety Parameters

Upon completion of the study imaging, subjects will be contacted to screen for adverse events after a period of 2 and 30 days from procedure. Patients with abnormal clinical findings will be followed until the condition resolves or stabilizes. Adverse events or serious adverse events that occur during the follow-up period will be recorded regardless of relatedness to the study procedure. The safety follow-up may be conducted by a phone visit or a clinic visit; if clinically indicated, a clinic visit should be performed along with relevant lab work.

Patients will be contacted by phone at 1 and 2 years for follow up evaluation. See MOP for details.

We anticipate most AE/SAEs will be related to anoscopy (pain, bleeding). Proflavine has been administered to >1000 patients for use with HRME imaging

under [name] studies and we have had 0 related adverse events or serious adverse events.

7.3 Adverse Events and Serious Adverse Events

Possible risks associated with the study procedures are listed below. There may also be risks that are not known.

Allergic reaction

There is the possibility of an allergic reaction to the Proflavine contrast dye in which participant may have local irritation. The participant can receive antihistamines and other anti-allergy medications if this happens.

Specimen Imaging Probe

There are no known risks from the use of the imaging probe.

Anal biopsies

The risk for anal biopsies are pain, bleeding, and infection. The biopsies are part of the standard of care procedure and would be obtained regardless of study enrollment. It is important that the participant tell the study staff about any side effects that he/she may have had even if he/she does not think it is related to the procedure. Because these patients will all have abnormal anal cytology, the HRA is a standard-of-care procedure.

Pregnancy

Insufficient information is available on the use of Proflavine in pregnancy. Drugs can have harmful effects on the fetus at any stage of pregnancy.

Loss of Privacy

Subjects will be consented on the day of their procedure. Subjects will be taken to a private area where the study information will be discussed. No additional sensitive information will be requested from the subjects beyond what is required to perform a standard study.. Subjects will be given an ID number for all forms, images, and communications. All data will be coded. Source documents will be redacted of all PHI before being sent from outside sites for data monitoring/data entry in the database. All PHI collected on BCM subjects will be stored in locked cabinets or password-protected files/computers where only the PI and study coordinator can see the names. All case report forms will use the assigned subject ID. Since the subject participation is only for one visit, there will be limited opportunity for privacy interests to arise between study recruitment and end of the study. The only extra intrusion of privacy will be an additional phone call at 2 and 30 days after the procedure to ensure that the subject has not suffered any adverse events. During the follow-up, only the study coordinator and/or the PI will have contact with the subject. Information pertaining to the study will only be discussed with the subject and messages containing identifiers of the subject's participation will not be left on voice-mail messages

7.4 **Reporting Procedures**

PI will inform local and IRB of record within 5 days of SAE reporting. AEs will be reported to the IRB annually at renewal. Any event that is reportable to IRB will also be reported to the DLDCCC Data Review Committee (DRC) via the Patient Safety Officer at [contact].

Any event that is reportable to the BCM IRB must also be reported by the BCM PI to the FDA via safety reports and in the annual report. Unexpected fatal or life-threatening adverse drug experiences will be reported within 7 calendar days. Serious and unexpected adverse drug experiences will be reported within 15 calendar days.

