9.2 Sample Size and Randomization

The study will primarily be powered to determine the precision around the operating characteristics of mHRME imaging. We estimate that because the median number of lesions per patient is approximately 1.5-2, and HSIL prevalence of 30%, approximately 150 patients (225-300) lesions will be needed to estimate the confidence intervals around SN and SP estimates see Table 1 below. In order for 150 patients to complete study procedures, we will target a total enrollment of 200, because we will also be improving the technology as a secondary objective and assume that up to 30% of patients may not have evaluable optimized HRME images.

Precision calculation

The damage to precision due to within-subject correlation is mitigated by the fact that the average number of per-patient slides is at most 2. Correlation = 0.5 is a high estimate, but the table below shows precision values close to the original independence-assumption based ones.

SN/SP estimate	¹ / ₂ width CI for 225 slides		¹ / ₂ width CI for 300 slides		
	indep	$\operatorname{corr} = 0.5$	indep	corr = 0.5	
10%	4.66%	6.99%	3.94%	5.91%	
15%	5.28%	7.93%	4.50%	6.75%	
20%	5.74%	8.61%	4.91%	7.37%	
25%	6.07%	9.10%	5.21%	7.82%	
30%	6.30%	9.46%	5.43%	8.14%	
35%	6.46%	9.69%	5.57%	8.35%	
40%	6.54%	9.81%	5.65%	8.47%	
45%	6.55%	9.82%	5.67%	8.50%	
50%	6.50%	9.74%	5.63%	8.45%	
55%	6.55%	9.82%	5.67%	8.50%	
60%	6.54%	9.81%	5.65%	8.47%	
65%	6.46%	9.69%	5.57%	8.35%	
70%	6.30%	9.46%	5.43%	8.14%	
75%	6.07%	9.10%	5.21%	7.82%	
80%	5.74%	8.61%	4.91%	7.37%	
85%	5.28%	7.93%	4.50%	6.75%	

Treatment Assignment Procedures

All participants will undergo HRME-imaging prior to biopsy

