9.6 Data Analyses

Objective 1. We will determine the performance characteristics of mHRME for the prediction of anal HSIL in flat mucosa and mucosal lesions using histopathology as the gold standard. Our hypothesis is that the sensitivity (SN) specificity (SP), positive predictive value (PPV) and negative predictive value (NPV), as well as the receiver operating curve for the identification of neoplasia on a per biopsy and per patient basis will be high. We will first compare the HRA-directed biopsy (as the gold standard) to the results of the mHRME HSIL diagnosis. The SN of mHRME diagnosis in detection of HSIL will be estimated with the binomial proportion of study participants who are positive for HSIL on HRA-guided biopsy at two thresholds of histology thresholds which are: 1) AIN 2+ threshold, and 2) AIN3+ threshold. SP will be estimated as the proportion of study participants who are negative for HSIL on HRA-guided biopsy at both thresholds. Positive and negative predictive values will be estimated using the binomial proportion and its 95% CI. In addition, the Cohens kappa statistic, and receiver operator characteristic curves will be generated if patient characteristics such as low CD4 count, cART utilization, or high HIV viral load impact the determination of SN and SP. The lab information will be collected and placed in the source document and entered in Oncore. SN and SP of mHRME-based HSIL diagnosis will be estimated on a per lesion and per patient basis with 95% confidence intervals and compared by McNemar's test. A generalized linear model for logistic regression with multiple correlated outcomes will compare SN and SP of each method on a per biopsy and per patient basis. For Device optimization: No Data Analyses are planned.

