 - a. Record scope in time, HRA start time (page 12)
 - b. Record first abnormal area as Biopsy 1 (page 13)
 - i. Describe lesion, mark location, take anoscopy image
 - ii. Record clinician HRA read, plan (standard of care)
 - c. Go onto second abnormal area as Biopsy 2 (page 14)
 - i. Describe lesion, mark location, take anoscopy image
 - ii. Record clinician HRA read, plan (standard of care)
 - d. Repeat above steps for each abnormal area using extra biopsy pages if necessary
 - e. Record HRA end time. Apply Proflavine, insert HRME. Record HRME start time.
 - f. Proceed to first abnormal area (Biopsy 1)
 - i. Once feed is in focus, freeze HRME
 - ii. Record clinician read and plan based on HRME image
 - iii. Analyze image. Record image number and score.
 - iv. Ask clinician if they are happy with this image or if they would like to take another. Take as many images as needed, using extra biopsy pages if necessary
 - v. Select best image of site (most representative)
 - g. Go onto Biopsy 2.
 - i. Once feed is in focus, freeze HRME
 - ii. Record clinician read and plan based on HRME image
 - iii. Analyze image. Record image number and score.
 - iv. Ask clinician if they are happy with this image or if they would like to take another. Take as many images as needed, using extra biopsy pages if necessary
 - v. Select best image of site (most representative)
 - h. Repeat above steps for each Biopsy using extra biopsy pages if necessary
 - i. Record end HRME time. Remove HRME attachment and insert biopsy forceps. Record biopsy start time.
 - j. Proceed to Biopsy 1, biopsy area. Place sample in labeled specimen container. Record specimen label.
 - k. Repeat for each biopsy.

- 1. Record biopsy end time.
- m. Record scope out time.

Within 2 Days of the Clinic:

20. Within 2 days of the procedure, CRC calls the study participant and complete the Follow Up Symptoms form. Be sure to provide the study participant with CRC and PI phone number (business card/consent form) in case of any adverse events. Any adverse events or serious adverse events reported during the phone call should be reported to PI within 24 hours of being reported. If applicable, the CRC and PI will complete the Serious Adverse Event form. The PI will inform the local and IRB of record if needed within 5 days.

Within 30 Days of the Clinic:

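### Section 7.3 treats every anal biopsy as standard of care, but 5.1 adds a normal-site biopsy for the study, and step 19 of the Manual of Operations has no step for it

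*Combined protocol and SAP*

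**What the plan says.** Section 7.3 names pain, bleeding and infection as the risks of anal biopsy, then states: "The biopsies are part of the standard of care procedure and would be obtained regardless of study enrollment".

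Section 5.1 describes two kinds of biopsy. Lugol's-negative (abnormal) areas are imaged and have "subsequent standard-of-care HRA biopsies at each image site". The next sentence, introduced as an addition, says "there will be at least one extra image and biopsy taken at a" Lugol's-positive (normal) site. It continues: "Each patient will likely have ≥ 2 biopsies". It then gives a total: "We plan to enroll 200 patients, which will yield 225-300 images".

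Sections 5.2 and 6.2 refer to the Manual of Operations in Appendix 1 for procedural detail. Its step 19 begins the site list with "Record first abnormal area as Biopsy 1 (page 13"), makes the second abnormal area Biopsy 2, and repeats this for each further abnormal area. The numbered sites are then imaged and biopsied in turn.

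Section 9.6 takes histology as the gold standard, and "SN and SP of mHRME-based HSIL diagnosis will be estimated on a per lesion and per patient basis".

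**The concern.** A biopsy that is extra to the standard-of-care biopsies, and taken where the mucosa looks normal, is not one the patient would have had without enrolling. The 7.3 sentence cannot be true of it. Because 7.3 is where the protocol sets out the risks of its procedures, someone relying on that section would attribute all biopsy risk to usual care and none to the study. The protocol's own introduction counts discomfort from unnecessary non-neoplastic biopsies among the drawbacks of current practice, so an added biopsy of normal mucosa is not a trivial matter on its own terms.

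The second strand is operational. If the working instruction has no normal-site step, the pair required by 5.1 may not be collected. Per-biopsy specificity and NPV would then rest only on sites that looked abnormal on HRA. If some staff took the pair and others did not, the mix of sites would vary.

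**Working it through.** This is mainly a comparison of texts; the arithmetic only sizes it.

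**Status of the biopsies.**
- 7.3: all biopsies are standard of care and independent of enrolment.
- 5.1, first sentence: standard-of-care biopsies at the imaged sites, which in that sentence are the Lugol's-negative areas.
- 5.1, second sentence: at least one further image and biopsy, at a Lugol's-positive site.

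The phrase about each image site belongs to the sentence on Lugol's-negative areas and does not reach forward to the normal site. The remark that closes the 7.3 paragraph calls the HRA standard of care; it does not say that biopsy of normal mucosa is. No other section reconciles 5.1 with 7.3.

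**Step 19 of the manual.**
- 19b to 19d create the list of numbered biopsies, every entry being an abnormal area.
- 19f to 19h image the numbered sites.
- 19j and 19k biopsy them.

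The instructions in 19h and 19k to repeat for each biopsy point back to that list. No step selects, images or biopsies a Lugol's-positive site.

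**The plan's own count.** Section 9.2 uses 150 patients and 1.5 to 2 lesions per patient: 150 × 1.5 = 225 and 150 × 2 = 300. This reproduces the 225-300 lesions in 9.2. Section 5.1 attaches the same range to 200 patients, that is 225 / 200 = 1.125 to 300 / 200 = 1.5 images per patient. That is below the two or more biopsies per patient expected in the same paragraph.

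**Number of study-added biopsies.** Inputs: 200 enrolled and 150 completing, from 9.2 ("In order for 150 patients to complete study procedures, we will target a total enrollment of 200"); one normal-site biopsy per patient, an assumption.
- Enrolled: 200 × 1 = 200.
- Completers: 150 × 1 = 150.

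The shortfall from 200 to 150 allows for images that cannot be evaluated. Patients with such images could still be biopsied, so for risk the base of 200 is the more relevant one.

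**Do the image totals already include normal sites?** One abnormal plus one normal image per patient gives 150 × 2 = 300, the top of the stated range, or 200 × 2 = 400, above it. The totals do not settle the question.

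**The case against.** The strongest reply is that 5.1, not 7.3, may be the text in error. Section 7.3 and step 19 agree with each other, the 9.2 count fits abnormal lesions alone, and the image total in 5.1 does not fit its own biopsies per patient. This is possible, and the fix allows for it. It is the weaker reading, because 5.1 is explicit about an extra biopsy at a normal site, and 9.6 sets out to assess flat mucosa as well as mucosal lesions. The conflict remains whichever text is wrong.

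It is also fair to say that no risk goes unnamed. Section 7.3 lists the biopsy risks, 5.1 describes the extra biopsy openly, and 4.2 excludes patients on platelet count and bleeding disorder. The fault is in which risk is credited to the study.

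Several stronger readings are tempting, and the documents do not support them:

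- *That adverse events from this biopsy would be missed or misattributed.* Sections 7.2 and 7.5 record events regardless of relatedness, and no rule assigns events to standard of care.
- *That participants are misinformed.* The consent pages are not among the material available, so this can only be checked by the sponsor.
- *That normal-site pairs will be omitted throughout the study.* The manual shown is headed for Thomas Street Clinic. Step 19 also has the coordinator complete CRF pages 11-20, which are not shown and may carry a normal-site field.
- *That specificity or NPV is therefore biased.* Section 9.6 does not say outright that normal-site pairs enter these estimates, and no effect can be quantified.
- *That a third or more of all biopsies are study-added.* One extra on top of 1.5 to 2 lesions would be 1 / 2.5 = 40% to 1 / 3 = 33%, but this needs a fixed one per patient and lesion counts that exclude normal sites. Neither is stated.

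**Conclusion.** The contradiction between 7.3 and 5.1 stands on the text alone: the standard-of-care statement is untrue of the normal-site biopsy that 5.1 adds, and 7.3 understates the study-added risk accordingly. The size is up to about 200 extra biopsies, assuming one per enrolled patient. The expectation of at least two biopsies each makes that the natural reading of 5.1, but it is not written there. With fewer, the number falls but 7.3 remains wrong for each one taken; because 5.1 says at least one, more than one per patient would raise it.

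The gap in the manual is real in step 19 as shown, but its consequence is conditional. Staff following it would omit the normal-site pair unless the CRF pages prompt for it, and the finding extends only to the site named in its heading. What would be lost is data that can contribute to specificity and NPV. Both parts should be corrected; neither calls the sample size or the analysis method into question.

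**What to change.** - **7.3:** limit the standard-of-care sentence to biopsies at Lugol's-negative sites. Add that the normal-site biopsy in 5.1 is study-specific and carries added risk of pain, bleeding and infection.
- **Manual of Operations, step 19:** add a step to select, image and biopsy a Lugol's-positive site, and confirm that the CRF has a place to record it and that the Mount Sinai procedure matches.
- **5.1:** state whether the normal-site pair is taken in every patient.
- **Participant information:** check that it describes the normal-site biopsy in the same way.

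If the sponsor no longer intends the normal-site biopsy, correct 5.1 instead and leave 7.3 and step 19 as they are.

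The cost is a reworded and an added sentence in 7.3, one procedural step, a few words in 5.1 and a document check. No procedure is added beyond those 5.1 already plans, and the sample size, analysis and visit schedule do not change.
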